### 3.4 Resveratrol and its role in treatment of LAM

Resveratrol (*trans*-3, 5, 4'-trihydroxystilbene) is a naturally occurring polyphenol found in grapes, berries, and red wine (19). Multiple studies have shown Resveratrol to have anticancer, anti-inflammatory, and anti-oxidant properties (19-23).

#### Resveratrol and mTOR regulation

Resveratrol has a complex mechanism of mTOR regulation. Resveratrol inhibits mTORC1 phosphorylation in a dose-dependent manner by inhibiting phosphorylation at S2448 residue (19, 24). Resveratrol has also been shown to have multiple effects on mTORC2 signaling (25). Resveratrol is believed to regulate mTOR activity through modulation of 5' AMP-activated protein kinase (AMPK), a key molecule for energy sensing that negatively regulates mTOR activity. Resveratrol induced phosphorylation of AMPK causes decreased phosphorylation of mTORC1 and its downstream targets (26). Resveratrol has also been shown to inhibit Akt phosphorylation in a dose-dependent and time-dependent manner, thus leading to mTORC1 inhibition (27). Lastly, Resveratrol has been shown to promote association between mTOR and DEPTOR, a negative regulator of mTORC1 and mTORC2 that inhibits mTOR kinase activity (28). The inhibition of PI3, Akt and mTOR activity has also been postulated to be responsible for the pro-apoptotic effects of Resveratrol (19).

#### Resveratrol and its role in regulating autophagy

[figure not shown]
Autophagy is an evolutionarily conserved process of recycling organelles or misfolded proteins that allows cells to maintain homeostasis under stress-induced conditions (29). Autophagy allows cancer cells to continue to survive by recycling intracellular components and persisting under low-nutrient or stress-induced conditions. The mTORC1 pathway is central to regulation of autophagy via its modulation of multiple autophagy-regulating factors such as Akt, AMPK, and S6K1. Resveratrol inhibits the activity of Akt, AMPK and S6K1, thus leading to autophagy down-regulation (19).

### **Sirolimus as a single agent may promote cell survival in LAM**

[figure not shown]
Results from the MILES trial show that sirolimus as a single agent can lead to stabilization of lung function decline in patients with LAM (12). However, lung function decline resumed at a rate similar to the placebo group after stopping sirolimus, suggesting a suppressive rather than curative effect of sirolimus in LAM. The inhibition of mTOR activity with sirolimus releases the negative feedback signaling from S6K to Akt. The resultant increased Akt activity prevents cancer cell death by protecting them from apoptosis. Additionally, *TSC2*-/- LAM cells are dependent on autophagy for survival, and, since mTORC1 is a major regulator of autophagy, inhibition of this pathway with rapamycin induces autophagy, paradoxically leading to cell survival (30).

### **Combination of Resveratrol and Sirolimus treatment restores inhibition of Akt, while suppressing mTORC1 signaling**

In a recent study, wild type and *TSC2* null mouse embryonic fibroblasts (MEFs) were treated with both Resveratrol and Sirolimus (30). Sirolimus effectively suppressed mTORC1 signaling in both cell types, as measured by markers of S6K1 activity. Due to inhibition of the negative feedback loop, Sirolimus treatment increased Akt signaling, as measured by phosphorylation of Akt and its target PRAS40. Resveratrol treatment alone suppressed basal Akt signaling and slightly decreased S6K1 pathway activation. Interestingly, Resveratrol was able to prevent rapamycin-induced reactivation of Akt signaling as well as phosphorylation of its downstream substrate, PRAS40, while simultaneously effectively suppressing mTORC1/S6K1 signaling (Figure 5). Similar results showing inhibition of Akt signaling and mTORC1 inactivation by a combination of Resveratrol and Sirolimus were replicated in uterine leiomyoma-derived smooth muscle cells, human LAM-derived *TSC2*-null 621-101 cells, and normal human bronchial cells (Images not shown) (30).

[figure not shown]
The effect of the combination of sirolimus and resveratrol on autophagy induction was studied in wild type and TSC2 null MEFs (30). Levels of p62/SQSTM1 protein inversely correlate with autophagy induction. While resveratrol alone did not have an effect on p62 levels, the combination treatment of sirolimus and resveratrol blocked autophagy induction in wild type and TSC2 null MEFs, and restored p62 levels back to baseline (Figure 6). Similar results showing a downregulation of autophagy were observed by treating human LAM-derived TSC2-null 621–101 cells with a combination of resveratrol and sirolimus (Images not shown) (30).

**Figure 6:** Resveratrol prevents sirolimus induced induction of autophagy. Wild type mouse epithelial fibroblasts (MEFs) and TSC2 null fibroblasts were treated with 20nM Sirolimus and 100 $\mu$ M Resveratrol for 24 hours. Cells were lysed and protein levels of p62 and actin were detected by immunoblot.

#### **Apoptosis is induced in TSC2-null cells, but not in control cells**

[figure not shown]
Wild type and TSC2 null MEFs were treated with sirolimus and/or resveratrol for 24h and assayed for apoptosis induction by examining cleavage of 2 markers, PARP and Caspase 3. Resveratrol treatment, alone or in combination with sirolimus, was able to strongly increase cleavage of PARP and Caspase 3 specifically in TSC2 null MEFs and not in wild type MEFs (Figure 7). These findings of increased apoptosis by resveratrol in TSC2 null cells were replicated in uterine leiomyoma-derived smooth muscle cells, human LAM-derived TSC2-null 621–101 cells (Images not shown) (30).

**Figure 7:** Resveratrol, alone or in combination with sirolimus, leads to apoptosis in TSC2 null mouse epithelial fibroblasts (MEFs) and not in wild type MEFs. Wild type and TSC2 null MEFs were treated with 20 nM rapamycin and/or 100  $\mu$ M resveratrol for 24 h. Cells were lysed and probed for PARP, cleaved-Caspase 3, and actin. The arrow indicates cleaved PARP isoform.

#### Combination of sirolimus and resveratrol reduces the metastatic capacity of uterine leiomyoma-derived smooth muscle cells

[figure not shown]
TSC2 null uterine leiomyoma derived smooth muscle cells (ELT3 cells), metastasize to the lungs following tail vein injection into mice replicating an *in vivo* model for LAM (31). After 24 h treatment, mice treated with the combination therapy of resveratrol and sirolimus had significantly fewer lung metastases as assayed by photon flux compared with control mice or mice treated with either sirolimus or resveratrol alone (Figure 8) (30).

**Figure 8:** Combination of sirolimus and resveratrol strongly reduces the survival of Tsc2-null cells *in vivo*. Mice were treated with vehicle, sirolimus, resveratrol, or sirolimus plus resveratrol. ELT3-luciferase-expressing cells were inoculated intravenously. Representative bioluminescent images of lung colonization at 1, 6, and 24 hours post-cell injection are shown above depicting a significant decrease in pulmonary metastases following treatment with combination of resveratrol and sirolimus.

### Combination treatment with resveratrol and sirolimus causes a significant reduction of TSC2 deficient xenograft tumor size and growth

Mice bearing ELT3-luciferase-expressing xenograft tumors were treated with sirolimus and resveratrol as single-agent treatments or in combination. There was no evidence of drug toxicity as evidenced by a lack of significant weight change among treatment groups. While sirolimus treatment alone showed a slight but significant reduction in tumor size in just 3 weeks of treatment, the combination of sirolimus and resveratrol caused [SEP] a statistically significant reduction in tumor size as compared with sirolimus treatment alone by as early as Week 2 [SEP] of treatment, and this reduction in tumor size was maintained at 4 weeks after treatment (Figure 9) (32).

[figure not shown]
**Figure 9:** Combination treatment with sirolimus and resveratrol reduces tumor size and inhibits growth. Female CB17-scid mice were inoculated with ELT3-luciferase cells subcutaneously. Mice were treated with vehicle, sirolimus, resveratrol, or a combination of sirolimus and resveratrol for 4 weeks. Bioluminescent intensity in xenograft tumors was recorded and quantified weekly. Vehicle- and resveratrol-treated tumors progressed faster than the tumors in sirolimus or sirolimus-resveratrol groups. Combination of sirolimus and resveratrol caused [SEP] a statistically significant reduction in tumor size as compared with sirolimus treatment alone.

### The Combination of Sirolimus and Resveratrol Suppresses PI3K/Akt/ mTORC1 Activation in the TSC2 deficient xenograft tumor

Mice bearing ELT3-luciferase-expressing xenograft tumors were treated with sirolimus and resveratrol as single-agent treatments or in combination. The combination of sirolimus and resveratrol resulted in severe reduction of S6 phosphorylation and approximately 40% inhibition of 4EBP1 phosphorylation. Sirolimus alone resulted in mild reduction of S6 phosphorylation. Moreover, the combination of sirolimus and resveratrol caused a 45% inhibition of Akt phosphorylation at S473, with no effect on p-ERK signaling, thus indicating the specificity of this treatment in inhibiting Akt/mTORC1 signaling (32).

### Combined Administration of Sirolimus and Resveratrol Reduces Proliferation and Induces Apoptosis within the TSC2 deficient xenograft tumor

[figure not shown]
Mice bearing ELT3-luciferase-expressing xenograft tumors were treated with sirolimus and resveratrol as single-agent treatments or in combination for 4 weeks. Sirolimus and resveratrol combination treatment caused a 2-fold up-regulation of cleaved caspase-3, a marker of apoptosis. In addition, analysis of TUNEL staining of tumor sections showed that combination treatment increased the levels of apoptotic TUNEL-positive cells by 3-fold, whereas single-agent treatment with either sirolimus or resveratrol had no effect on apoptosis (Figure 10). Taken together, these data indicate that a 4-week administration of the combination treatment of sirolimus and resveratrol inhibits mTORC1 signaling, inhibits Akt activation, and induces apoptosis (32).

[figure not shown]
**Figure 10:** The combination of rapamycin and resveratrol induces apoptosis in xenograft tumors. TUNEL: terminal deoxynucleotidyl transferase dUTP nick end labeling.

### 3.5 Role of home spirometry in pulmonary disorders

In a recent study, 50 patients with idiopathic pulmonary fibrosis (IPF) performed daily home spirometry for a median of 279 days. Office-based spirometry was performed 6- and 12-months after enrollment. In this study, over 80% of the patients adhered to the routine of performing daily spirometry, daily spirometry values showed excellent correlation with office-based spirometry (Figure 11), and the rate of decline in FVC obtained after 3 months of home spirometry was highly predictive of patient outcomes and subsequent mortality (HR: 1.04, CI: 1.02–1.06,  $p<0.001$ ) (Figure 12) (33).

**Figure 11:** Bland-Altman plots demonstrating good agreement between office-based measurements of FEV1 (left) and FVC (right) with home-based measurements. There was a slight bias (0.20 liters) towards consistently higher readings obtained during office-based measurements as opposed to home-based measurements

**Figure 12:** Kaplan-Meier curve demonstrating that the trends obtained from home-based FVC monitoring are predictive of the overall survival in patients with IPF. Left: Increased mortality in patients with FVC decrease more than 5% from baseline after 3 months of monitoring. Right: Increased mortality in patients with FVC decrease more than 10% from baseline after 12 months of monitoring.

Johannson et al. were able to achieve a compliance rate of 90% with once-weekly home spirometry in 24 patients with IPF, and demonstrated that weekly home spirometry is both reliable and feasible in this patient population. Addition of weekly home spirometry resulted in enhanced precision, and was estimated to reduce the sample size needed to study the efficacy of a new intervention by four-fold (34). In another recent study, patients with cystic fibrosis randomized to twice-weekly home spirometry measurements had a statistically significant shorter time to detection of disease-related exacerbations as opposed to usual care. However, the adherence to home spirometry in this study was suboptimal with 50% of the population consistently performing once-weekly testing, and only 19% of the population adhering to the twice-weekly regimen (35). Home spirometry has been shown to facilitate early detection of bronchiolitis obliterans following lung transplantation as compared to office-based spirometry (36, 37).

### **3.6 Rationale for the proposed study**

Treatment with sirolimus alone has a suppressive rather than remission inducing effect. In addition, mTORC1 inhibition by sirolimus leads to upregulation of autophagy and paradoxically increases LAM cell survival. As explained in Section 3.4, the combination of resveratrol and sirolimus is effective in blocking autophagy and inducing apoptosis of *TSC2*−/− cells, as well as reducing their survival *in vivo* with minimal effect on normal, *TSC2*-expressing cells. These pre-clinical results form the rationale for investigating the combination of resveratrol and sirolimus as a treatment option for patients with LAM and TSC. Since there is no clinical data on the adverse effect profile and effective dosing of resveratrol in patients with LAM, we plan to conduct a phase II, dose escalating, safety and efficacy study of resveratrol in combination with sirolimus with plans for a multi-center phase III study after successful completion of this project.

Home spirometry has the potential to shorten the length of monitoring time needed to determine the disease trajectory. Reliable estimates of lung function typically require multiple measurements (3 or more) obtained over a prolonged monitoring period, usually 12 months or more. We hypothesize that the trajectory of lung function decline and treatment response can be determined in a much shorter period of time using frequent home-based spirometric measurements. Our strategy of testing home spirometry in conjunction with RESULT will allow us to directly compare home spirometry to standard office-based spirometry in an ATS/ERS calibrated laboratory and with real time quality control for both home- and office-based pulmonary function studies. Our project will validate the use of home spirometry as a novel disease-monitoring tool for patients with LAM, and will help integrate home spirometry in clinical practice, and in future studies seeking to develop novel treatment approaches.

## **4. Study Objectives and Endpoints:**

### **4.1 Primary Endpoint:**

The primary objective of this study is to assess the change in serum vascular endothelial growth factor-D (VEGF-D) value after 24 weeks of treatment with a combination of resveratrol and sirolimus, as compared to the VEGF-D value on sirolimus alone.

### **4.2 Secondary Endpoints:**

1. Safety and adverse effect profile of combined resveratrol and sirolimus in patients with LAM
2. Mean change in FEV1 before and after treatment
3. Mean change in FVC before and after treatment
4. Difference in rate of change in FVC (slope) before and after treatment
5. Difference in rate of change in FEV1 (slope) before and after treatment
6. Mean change in diffusion capacity of carbon monoxide (DLCO) before and after treatment
7. Difference in rate of change in DLCO (slope) before and after treatment
8. Baseline to 24-week change in the score on St. George's Respiratory Questionnaire (SGRQ)
9. Baseline to 24-week change in the score on ATAQ-LAM (A tool to assess quality of life in LAM)
10. Baseline to 24-week change in the score on SD-SOB score (San Diego Shortness of Breath Questionnaire)
11. Baseline to 24-week change in the score on EuroQOL scale
12. Overall compliance with weekly home spirometry.
13. Correlation between home spirometry values (absolute as well as trends) with office-based spirometry values and trends.

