## 6. Study Procedures and Timelines

### 6.1 Study and Timeline Overview

Patients will be identified by the medical and research staff at the LAM clinic at the University of Cincinnati Medical Center. Study staff will screen up to 60 patients over 15 months with a goal of enrolling 25 participants. Patients who meet eligibility criteria, provide informed consent and are enrolled in the study will receive instructions regarding resveratrol dosage, route and administration. An 8-week supply of resveratrol will be provided at visit 1. Patients will begin resveratrol at a starting dose of 250mg daily, and increase the dose in two increments to a maximum dose of 1000mg daily. If patients do not tolerate a certain dose of resveratrol, the dose will be reduced to the last tolerated strength. Patients will remain on the last well-tolerated dose of resveratrol for the entire study duration. Patients who are unable to tolerate the lowest dose of resveratrol will be withdrawn from study.

The patients will be given a copy of the informed consent form. Patients will be given ample time to read and discuss the consent form with the study staff. The study staff will then answer any remaining questions asked by the patients. The patients will be offered the option of signing the consent form. Those who agree to participate will undergo the remainder of screening visit.

Prior to starting study drug, pre/post bronchodilator spirometry, diffusion capacity of carbon monoxide (DLCO), and serum VEGF-D will be obtained to establish baseline values prior to study drug initiation. The best values for FEV1 and FVC obtained during the spirometry maneuvers will be used. Patients will be followed with serial spirometry and VEGF-D levels collected at the initial visit, followed by week 8, week 16 and week 24 visits. DLCO will also be obtained at the 24-week visit in addition to spirometry.

For patients who agree to the home spirometry study, we will teach them on the proper technique to perform, record and transmit home spirometry, and provide them with a home spirometer. The patients will perform their first test during the initial visit and we will use those values to compare the home spirometer values with the office-based spirometry values. After that patients will be instructed to perform home spirometry once a week as detailed in Section 5.7.

Section 6.2 provides a summary of the study timeline and procedures.

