## 6.2 Schedule of Events:

Event	Screening Visit*	Initial Visit	Week 2	Week 4	Week 8	Week 12	Week 16	Week 18	Week 20	Week 24
Visit number	0 or Phone	1	Lab check	Phone	2	Phone	3	Lab check	Phone	4
Informed consent	X									
History and physical		X			X		X			X
CBC, CMP		X			X		X			X
Lipid panel		X			X					X
Serum VEGF-D	X	X			X		X			X
Sirolimus level		X	X***	X***	X	X***	X	X***	X***	X
Urine Pregnancy Test**		X			X		X			
Saved serum and plasma		X			X		X			X
Spirometry post BD		X			X		X			X
Diffusion capacity		X								X
Home spirometry dispensed		X****								
Review concomitant meds		X		X	X	X	X		X	X
Review adverse events				X	X	X	X		X	X
SGRQ		X			X		X			X
ATAQ-LAM		X			X		X			X
EuroQOL		X			X		X			X
SD-SOB		X			X		X			X

Window for all visits after the initial visit:  $\pm 7$  days, except Weeks 2 and 18 where the window is  $\pm 3$  days

\* Screening visit can be the initial visit if a patient meets all inclusion/exclusion criteria. Informed consent for study inclusion can be obtained remotely over the phone rather than in-person. VEGF-D levels to confirm eligibility for trial participation can be drawn remotely rather than an in-person visit.

\*\* Only required for women of childbearing potential.

\*\*\* Can be drawn remotely. This is a trough level to be obtained  $24 \pm 4$  hours after the last sirolimus dose.

\*\*\*\* FEV1 and FVC will be obtained once weekly from patients agreeing to participate in the home spirometry sub study. Detailed instructions regarding the proper use of the home spirometer will be provided at the time of enrollment, along with access to detailed instruction manuals for future use. Once a week, patients will perform at least three spirometric measurements at approximately the same time, and record the best FEV1 and FVC values as their weekly results. These results, along with the associated flow-volume and volume-time loops will then be transmitted electronically to the study coordinator.

ATAQ-LAM: A Tool to Assess Quality of Life in LAM, BD: Bronchodilators, CBC: complete blood count, CMP: comprehensive metabolic panel, SGRQ: St. George's Respiratory Questionnaire, SD-SOB: San Diego Shortness of Breath scale, VEGF-D: Vascular Endothelial Growth Factor-D.

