## 6.3 Study Visits

### Screening/Initial Visit

At the screening visit, the consent form will be presented to the potential patient. If the patient is competent to understand the risks, agrees to participate and provides informed consent and HIPAA release, the patient will undergo screening. Patients will also be informed about the home spirometry portion of this study, and given the option to opt-in or opt-out of the home spirometry evaluation. Patients may enroll in the clinical trial without agreeing to participate in the home spirometry portion. During this visit, we will review the inclusion/exclusion criteria, obtain a urine pregnancy test for women of childbearing potential (defined as any fertility status other than natural or surgical menopause or post hysterectomy), and check a serum VEGF-D level (if two previous stable values post initiation of sirolimus are not drawn). The screening visit and VEGF-D testing can be accomplished either remotely or in-person. If patients meet the study inclusion criteria, the screening visit can be their initial study visit. We anticipate that in most patients the screening visit will be the initial study visit, and the following additional steps will be completed during the visit:

- Review current medications.
- Review medical history and conduct a physical examination.
- Perform spirometry with appropriate safety precautions. All spirometry tests during all visits will be performed after supervised administration of bronchodilator in the pulmonary function laboratory.
- Perform diffusion capacity (DLCO) testing. DLCO will be performed in a supervised setting in the pulmonary function laboratory.
- Obtain clinical labs including: complete blood count (CBC), comprehensive metabolic panel (CMP), lipid panel, serum VEGF-D, sirolimus level, urine pregnancy test, and urinalysis.
- Quality of life, dyspnea and fatigue assessments
- Dispense resveratrol tablets for the next 8 week supply.

- Provide a drug diary to document drug compliance. Patients will bring the drug diary at each subsequent visit
- If the patient has consented obtain a blood sample to be stored on-site for potential future use

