- If the patient has consented, instruct them on the proper technique to perform home spirometry, provide them with a home unit, and obtain the first set of FEV1 and FVC values. Patients will also be taught on how to record and transmit electronically the home spirometry values on a weekly basis throughout the 24-week trial duration.

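### Secondary endpoints 4, 5 and 7 compare lung-function slopes before and after treatment, but the plan collects only one pre-drug time point per measure, so these differences have no estimate

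*Combined protocol and SAP*

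**What the plan says.** Section 4.2 separates changes in level from changes in slope. Endpoints 2, 3 and 6 are mean changes in FEV1, FVC and DLCO. Endpoint 4 is "Difference in rate of change in FVC (slope) before and after treatment", endpoint 5 repeats this for FEV1, and endpoint 7 is "Difference in rate of change in DLCO (slope) before and after treatment".

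The data behind them are set out in sections 6.1 to 6.3:

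- **Baseline.** "Prior to starting study drug, pre/post bronchodilator spirometry, diffusion capacity of carbon monoxide (DLCO), and serum VEGF-D will be obtained to establish baseline values" (section 6.1). This is a single set of measurements.
- **Office spirometry.** Section 6.1 plans "serial spirometry and VEGF-D levels collected at the initial visit, followed by week 8, week 16 and week 24 visits".
- **DLCO.** Sections 6.1, 6.2 and 15 (Specific Aim 3) place it at the initial visit and week 24 only.
- **Screening.** The screening column of the section 6.2 schedule has consent and VEGF-D, and no lung function. Section 6.3 expects screening and initial visit to coincide in most patients.
- **Drug start.** The initial-visit list in section 6.3 includes "Dispense resveratrol tablets for the next 8 week supply".
- **Home spirometry (optional).** "The patients will perform their first test during the initial visit" (section 6.1). At that visit staff "obtain the first set of FEV1 and FVC values" (section 6.3).

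In section 15, Specific Aim 3 applies the VEGF-D analysis to lung function, and that analysis compares follow-up values with baseline. The home spirometry paragraph adds a mixed-model FEV1 slope over time and a comparison of the 8-week with the 24-week rate of decline.

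**The concern.** The three endpoints are the plan's only stated within-patient comparison of lung-function trajectory on the combination with trajectory on sirolimus alone. If the before slope has no data source, the plan does not say what would be reported in its place. The choice between omitting the endpoints, searching charts and reporting on-treatment slopes would then fall during or after an open-label, single-arm trial, when results may be visible. An on-treatment slope published under these labels could be taken for a before/after comparison that was never made. The trial is meant to inform a phase III study, so that misreading could carry forward.

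**Working it through.** The plan gives no figure for these endpoints to reproduce. The check is whether the scheduled times identify the quantity named.

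**Step 1. Count time points relative to the first dose (day 1 = week 0).**

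| Measure | Scheduled weeks | Pre-drug | On drug |
|---|---|---|---|
| FEV1, office | 0, 8, 16, 24 | 1 | 3 |
| FVC, office | 0, 8, 16, 24 | 1 | 3 |
| DLCO | 0, 24 | 1 | 1 |
| FEV1 and FVC, home | 0, then weekly to 24 | 1 | 24 |

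The minimum for a before slope is 2 pre-drug values. Visit timing cannot supply the second: section 6.2 gives a "Window for all visits after the initial visit", and at ±7 days (±3 days at weeks 2 and 18) every such visit remains after drug start.

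**Step 2. Write the model the endpoint needs.**

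E[Y(t)] = a + b·min(t, 0) + c·max(t, 0)

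Here a is the level at drug start, b the slope before and c the slope after. The endpoint is c − b. There are 3 parameters.

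**Step 3. Put in the scheduled times.** The design rows (1, min(t,0), max(t,0)) for office spirometry are:

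- t = 0: (1, 0, 0)
- t = 8: (1, 0, 8)
- t = 16: (1, 0, 16)
- t = 24: (1, 0, 24)

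The middle column is all zeros, so the rank is 2. The parameters a and c are identified; b, and therefore c − b, is not. The other cases are:

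- DLCO, rows (1, 0, 0) and (1, 0, 24): rank 2 of 3.
- Home spirometry, weekly 0 to 24: rank 2 of 3.
- Office schedule pooled over 25 patients: rank 2 of 3. Neither more patients nor a mixed model helps.
- Tests after study exit added (illustrative weeks 52, 76, 128): rank 2 of 3.
- One earlier test added (illustrative week −24): rank 3 of 3 for spirometry and for DLCO.

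The last line shows that the missing item is a pre-drug value.

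**Step 4. Look for another source of pre-drug values.**

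- Section 5.2 requires earlier serial values for VEGF-D only.
- Section 6.7 record review is optional and covers the time after the patient leaves the study.
- Section 16.1 transfers clinical results to CRFs without naming earlier lung-function tests.
- Section 18 draws on electronic notes from research encounters.

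**Step 5. Look for the contrast in the analysis plan.** The slope comparisons given are 8-week versus 24-week home spirometry (section 15) and home versus office trends (endpoint 13 and the synopsis). Both use on-treatment follow-up.

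**Step 6. See what can be estimated.** On-treatment FEV1 and FVC slopes can be, from four scheduled office values. A DLCO slope rests on two values: for a week-24 completer, slope per year = (24-week change) × 52/24 = 2.17 × endpoint 6. It is endpoint 6 in other units.

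**The case against.** Three points can fairly be made for the plan.

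*The wording may be loose.* Endpoints 2, 3 and 6 also say before and after treatment and mean an ordinary baseline-to-end change, and section 15 defines slope as one rate over time. Endpoints 4, 5 and 7 may be imprecise labels for on-treatment slopes. This is possible, but a difference in rate of change fits it poorly. If it is right, the endpoints still need rewording, as in the first option under the fix.

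*Earlier tests probably exist.* Section 9.2 says LAM patients routinely have breathing tests in clinical care, section 5.1 recruits through the site's own LAM clinic, and the initial visit includes a history review. The CRFs are not among the documents. This stands in part: a reader might infer that a before slope is impossible, and the documents do not support that. The defect is that the plan neither names a source nor orders collection, so following it as written yields no estimate.

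*The stakes are limited.* Section 14 calls the trial exploratory, and these are secondary endpoints. That is fair.

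A reader might also infer that the trial can say nothing about lung-function trends, or that off-drug data are confined to patients who stop early. Neither follows. On-treatment FEV1 and FVC slopes are estimable, and the optional review in section 6.7 could bring post-exit tests from completers as well. Post-exit tests still give no before slope.

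**Conclusion.** The point holds for the data the plan says it collects. None of the 3 slope differences (endpoints 4, 5 and 7, out of 13 secondary endpoints) can be estimated: each measure has 1 pre-drug time point where at least 2 are needed, and the design has rank 2 for 3 parameters. The result depends on the visit schedule and on a slope requiring two dated values. It does not depend on any assumed variance, effect size or sample size. It would change only if pre-enrolment lung-function tests were collected, which the documents do not provide for. The primary VEGF-D endpoint and endpoints 2, 3 and 6 are unaffected. The sponsor should correct this, but it does not undermine the trial's main aim.

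**What to change.** Choose one of two options before analysis and write it into sections 4.2 and 15.

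**Option 1: report what the schedule supports.** Redefine endpoints 4 and 5 as the on-treatment FVC and FEV1 slopes from the initial visit to week 24. Estimate them with a linear mixed model of the office values, of the kind section 15 already gives for FEV1 under home spirometry. State that they are not a comparison with sirolimus alone. Drop endpoint 7, since with two DLCO values it only rescales endpoint 6. The cost is a wording change. It gives up the before/after slope claim, which the scheduled data cannot support.

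**Option 2: keep the before/after contrast.** Add abstraction of existing, dated lung-function tests from each patient's on-sirolimus period before day 1. Fix the look-back window and the minimum number of values. Section 3.6 says that 3 or more measurements, usually over 12 months or more, are typically needed, whereas section 5.2 guarantees only 20 weeks on sirolimus. Fit a mixed model with a knot at day 1, and report how many patients contribute a before slope. The cost is chart abstraction for up to 25 patients and a check that the consent covers earlier records, with no added visits or tests. The historical data will be uneven, and the contrast will be imprecise and still uncontrolled.
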